Penn Alcohol Craving Scale (PACS). The PACS is a clinical tool for practitioners to measure alcohol craving. It is a five-item self-administered instrument that measures frequency, intensity, and duration of thoughts about drinking along with ability to resist drinking. The final item asks the responder to provide an average rating of his or her craving over the course of the past week. The PACS has excellent internal consistency (Cronbach's $\alpha = 0.92$). Construct, predictive, and discriminant validity has also been established. This assessment takes between two and five minutes to complete (Flannery, Volpicelli, & Pettinati, 1999). The PACS will be administered as part of the post-test assessment.

Functional Outcomes of Sleep Questionnaire (FOSQ-10). The FOSQ-10 is a 10-item abbreviated version of the original 30 item instrument used to evaluate quality of life in relation to daytime sleepiness. The 30-

Protocol Number: 18-CC-0079

item questionnaire measures difficulty in performing tasks from five domains due to sleepiness or tiredness: General Productivity, Activity Level, Vigilance, Social Outcome, and Intimacy and Sexual Relationships (Weaver et al., 1997). The FOSQ-10 consists of two questions from General Productivity subscale, three from Activity Level, three from Vigilance, and one each from Social Outcome and the Intimacy and Sexual Relationships subscales. The 10-item version demonstrates high internal consistency similar to that of the original instrument (Cronbach's $\alpha = 0.87$), high correlation with the 30-item version of the scale, and the ability to detect a wide range of functional limitations (Chasens, Kampman, & Weaver, 2009). To obtain the total score for the FOSQ-10, the mean-weighted item score is calculated for each subscale. These subscale scores are then averaged and the mean was multiplied by five. Lower scores are indicative of higher levels of dysfunction. The FOSQ-10 will be administered at pre- and post-test time points.

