Epworth Sleepiness Scale (ESS). The Epworth Sleepiness Scale (ESS) is an eight-item self-administered questionnaire that provides a measure of an individual's general level of excessive daytime sleepiness over a one week time period (Johns, 1991). Individuals are asked to rate their usual chances of dozing off or falling asleep on a four-point scale in eight distinct situations or activities that most people engage in during their daily lives. Higher scores are indicative of higher levels of daytime sleepiness. An alpha coefficient between 0.70 to 0.88 has been documented and numerous studies support high validity and reliability (Spira, Beaudreau, Stone, et al., 2012; Johns, 1992). A score higher than ten is indicative of excessive daytime sleepiness (Johns, 1993). Completing the ESS generally takes two to three minutes.

Self-Efficacy for Sleep Scale (SE-S). The SE-S includes nine items used to measure the level of confidence a person has in performing behaviors that might be helpful in initiating sleep. Each item is scored on a five-point Likert scale from 1 representing "not confident" to 5 representing "very confident." The total score ranges from nine to 45, with higher scores indicative of greater confidence. Concurrent validity of the scale was established by comparison with PSQI, sleep diaries, and objective measures of sleep (Edinger, Wohlgemuth, Radtke, Coffman, & Carney, 2007). The scale has excellent internal reliability (Cronbach's alpha of 0.71-0.86; Edinger, et al., 2007; Rutledge, La Guardia, & Bluestein, 2013). Test-retest reliability has also been established (Fichten, Libman, Creti, Amsel, Sabourin, Brender, & Bailes, 2001). The SE-S was shown to be a significant predictor of sleep quality (unpublished data); increased self-efficacy for sleep was associated with better sleep quality (Brooks et al., unpublished data).

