2.5 Inclusion and Exclusion Criteria

2.5.1 Participants will be eligible for this study if they:

- Are 18 – 65 years old
- A score of 10 or higher on the Insomnia Severity Index*
- Are admitted as a treatment-seeking inpatient on 1SE under protocol 14-AA-0181 (signing both the clinical and research consent)
- Have been inpatient for at least 14 days prior to consent/screening
- Can speak, understand, and write in English
- Are able to comply with study requirements (including ability to access the Internet at least 2x per week)

2.5.2 Participants will be ineligible for this study if they:

- Are pregnant
- Are a prisoner
- Report a physician diagnosis of moderate to severe obstructive sleep apnea (OSA) OR test positive for moderate to severe OSA as documented with an Apnea Hypopnea Index of 15 events/hour based on WatchPAT testing results
- Have irregular sleep schedules that prevent the ability to follow treatment recommendations (i.e. usual bedtimes outside of 8:00 pm to 2:00 am or arising times outside of 4:00 am to 10:00 am)
- Meet SCID-5/DSM-5 criteria for opioid use disorder in the past year
- Meet SCID-5/DSM-5 criteria for severe cocaine use disorder and/or severe cannabis use disorder in the past year
- Meet diagnostic criteria for an unstable or serious psychiatric condition (schizophrenia, bipolar, major depressive disorder not currently in remission) - based on diagnosis from the SCID for DSM-5
- Are participating in any experimental pharmacological intervention study
- Presence of unstable or serious medical/neurologic illness at PI and MAI discretion

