Phase II: 60 participants - the total sample size for phase II of this study will test the primary hypotheses associated with the analysis plan. With insomnia severity as the primary outcome, we will use a two-sided alternative hypothesis that the rate of change will be different between the intervention group and the control group. Assuming a correlation of 0.6 between the two time points, an alpha level of 0.05, a power level of 0.8, and an estimated attrition rate of 40 percent, we will be able to detect an effect size of 0.84 with 60 participants (Fitzmaurice, Laird, & Ware, 2012). Permuted block randomization with block size of four will be used to equally assign participants in each group. The statistician, who will not have any contact with participants, will prepare the randomization sequences and give out the allocation assignment after each participant is consented.

Mixed model for repeated measure with group, time, and the interaction of group by time will be used to test the changes of insomnia severity in two groups. Mixed model for repeated measures will also be used to test the secondary objectives with potential covariates in the model. Demographic, psychiatric, and/or drinking-related factors significantly related to the outcomes listed in the secondary objectives will be entered in the model. Aikake information criterion and the Bayesian information criterion will be used to select best-fitting models. A potential dosing effect analysis including the number of cores completed as a covariate will be conducted for the treatment group only. With the linear mixed model approach, all available data points will be included in the analyses. Under missing completely at random and missing at random assumptions, linear mixed model with restricted maximum likelihood estimation can produce unbiased estimators (Salim, Mackinnon et al. 2008).

Investigator Conflicts: NIH guidelines on conflict of interest have been distributed to all investigators. NIH guidelines on conflict of interest have been distributed to all investigators.

Technology Transfer: No technology transfer agreement is in place for this protocol.

4 Rationale for subject selection

This study will be open to both males and females of all racial and ethnic groups, without targeting any specific group. We anticipate the target enrollment of participants to reflect the racial/ethnic distribution of residents in the greater Washington DC metropolitan area.

5 Recruitment plan

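### FOSQ-10 and ESS have a ward pre-test and an outpatient post-test, and Section 3 does not commit to a baseline-adjusted between-arm contrast, which would be at least as precise as group-by-time

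*Combined protocol and SAP*

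**What the plan says.** Section 1.2 lists daytime sleepiness and functional outcomes among the secondary outcomes. Section 2.4 states that "The FOSQ-10 will be administered at pre- and post-test time points", and its Table of Measures marks the ESS at the same two visits only. The table puts the pre-test under its inpatient heading and the post-test under its outpatient heading. An inclusion criterion in Section 2.5.1 reads "Have been inpatient for at least 14 days prior to consent/screening".

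Section 2.4 describes the ESS as covering a one-week period and rating "eight distinct situations or activities that most people engage in during their daily lives". It describes the FOSQ as measuring difficulty, due to sleepiness or tiredness, in productivity, activity, vigilance, social life and intimacy.

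For the primary outcome, Section 3 says "we will use a two-sided alternative hypothesis that the rate of change will be different between the intervention group and the control group", tested in a mixed model with group, time and their interaction. It continues: "Mixed model for repeated measures will also be used to test the secondary objectives", with potential covariates. The covariates named are demographic, psychiatric and drinking-related. The baseline score is not among them, and no constraint on baseline means is stated.

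**The concern.** Both scales ask about ordinary activities. At pre-test the week covered by the ESS lies wholly within the inpatient stay, and some activities in the FOSQ-10 may be restricted there. By post-test the participant is an outpatient. If ward answers say little about outpatient life, the pre-post correlation on these scales could be low.

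With two visits and no baseline constraint, the group-by-time term is the difference between arms in mean change. That contrast gives the baseline full weight however well it predicts the outcome, so a poorly matched baseline adds variance. What is at stake is precision on two secondary outcomes in a small trial. There is also a point of reading: pre-to-post change within an arm mixes leaving the ward with any effect of the programme.

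**Working it through.** **1. The plan's own figure.** Inputs from Section 3: 60 participants allocated 1:1, 40% attrition, two-sided test, "an alpha level of 0.05, a power level of 0.8", and "Assuming a correlation of 0.6 between the two time points". The correlation is given for insomnia severity.

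- Post-tests per arm: 60 × 0.6 / 2 = 18.
- SD of change, in units of the outcome SD: √(2(1 − 0.6)) = 0.894.
- Required n per arm for 0.84: 2 × (1.960 + 0.842)² × 0.8 / 0.84² = 17.8, so 18; then 36 / 0.6 = 60.
- Reverse: detectable effect 2.802 × √(2 × 0.8 / 18) = 0.835, with power of 80.4% at 0.84.

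The stated 0.84 with 60 participants is reproduced as a change-score calculation. Baseline adjustment at the same correlation would give 2.802 × √(2 × 0.64 / 18) = 0.747. The sizing therefore does not assume adjustment.

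**2. Variance of the two contrasts.** Section 3 keeps all available data, so the pre-tests of participants who later drop out contribute. I assume every randomised participant has a pre-test: 30 pre-tests and 18 post-tests per arm. With correlation r, the variance per arm is:

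- group-by-time, unconstrained baseline: SD_post²(1 − r²)/18 + (SD_pre − r·SD_post)²/30
- baseline-adjusted or baseline-constrained: SD_post²(1 − r²)/18

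The extra term is a square, so it is never negative. Apart from one degree of freedom, adjustment cannot be less precise, whatever r and the SDs are.

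**3. Size with equal SDs.** Relative to comparing post-tests alone (1.00), group-by-time is (1 − r²) + 0.6(1 − r)², where 0.6 = 18/30, and adjustment is 1 − r².

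| r (assumed) | Group-by-time | Adjusted | Variance saved |
|---|---|---|---|
| 0.6 | 0.64 + 0.096 = 0.736 | 0.64 | 13% |
| 0.4 | 0.84 + 0.216 = 1.056 | 0.84 | 20% |
| 0.3 | 0.91 + 0.294 = 1.204 | 0.91 | 24% |
| 0.2 | 0.96 + 0.384 = 1.344 | 0.96 | 29% |

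Group-by-time becomes worse than ignoring baseline when 0.6(1 − r)² exceeds r², that is, below r of about 0.44.

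**4. Illustrative power at r = 0.3.** I use an effect of 0.68 SD, which Section 3 cites for sleep efficiency. It is not a FOSQ-10 or ESS effect. Normal approximation:

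- Group-by-time: SE = √(2 × 1.204 / 18) = 0.366; 0.68 / 0.366 = 1.86; power about 46%.
- Adjusted: SE = √(2 × 0.91 / 18) = 0.318; 0.68 / 0.318 = 2.14; power about 57%.

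**5. If the ward SD is narrower.** Take SD_pre at half of SD_post. At r = 0.3 the extra term is 0.6 × (0.5 − 0.3)² = 0.024, so 0.934 against 0.91, a saving of 2.6%. At r = 0.6 it is 0.6 × (0.5 − 0.6)² = 0.006, so 0.646 against 0.64, under 1%. The gain can be close to nil, but it does not reverse.

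**The case against.** The strongest reply is that no loss from the change of setting has been shown. The documents give neither a correlation nor an SD for either scale. The only correlation stated, 0.6 for insomnia severity, is above the break-even point. The ESS is described as asking about usual chances of dozing, so some participants may answer about life outside the ward. The FOSQ-10 has no stated recall period and asks about difficulty caused by sleepiness, not about whether the activity took place. Under the scoring in Section 2.4 the single social and single intimacy items together carry two of five subscales, or 40% of the total. That weight applies at both visits and says nothing about the correlation. All of this stands: a low correlation is a possibility, not a documented fact.

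It is also fair that group-by-time is stated only for insomnia severity. The allowance for covariates does not exclude the baseline score, and no within-arm test on these scales is planned. The gap is therefore one of specification. Nor is the inpatient-to-outpatient pattern special to these two scales: DBAS-16, SE-S, IDS, Trait Anxiety and MFSI-SF share it, and changing two scales alone would make the plan inconsistent.

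A reader might take the penalty to be larger by treating the plan as complete-case change scores, with relative variance 2(1 − r), for example 1.40 at r = 0.3. Section 3 does not support that, because its model retains all available data; the figure is then 1.204. A reader might also infer that the move from ward to community biases the treatment comparison. It does not do so by itself, because both randomised arms make the same move.

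What survives is that adjustment uses data already collected and is never less precise, which does not depend on the unknown correlation.

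**Conclusion.** The point holds as a low-cost improvement to an under-specified analysis. For FOSQ-10 and ESS, an unconstrained group-by-time contrast does not use the baseline efficiently, and may do worse if the change of setting lowers the pre-post correlation. With equal SDs, 30 pre-tests and 18 post-tests per arm and data missing at random, adjustment saves about 13% of the variance at r = 0.6, rising to 29% at r = 0.2. At r = 0.3, power for an illustrative 0.68 SD effect is about 57% instead of 46%. With a much narrower ward SD the saving could be negligible.

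The documents do not show that precision is in fact lost because of the ward baseline. They also give no reason to think the between-arm comparison biased or the sample size wrong: the trial is sized on insomnia severity, and these are secondary outcomes. Within-arm change on these scales should not be read as a programme effect, whatever the correlation.

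**What to change.** In Section 3, pre-specify for FOSQ-10 and ESS, and for consistency the other scales taken only at pre- and post-test (DBAS-16, SE-S, IDS, Trait Anxiety, MFSI-SF), a between-arm contrast at post-test. It should come from a mixed model with baseline means constrained equal across arms, or with the pre-test score as a covariate. The constrained form fits the existing commitment to all available data more closely, since it keeps the pre-tests of participants without a post-test.

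Add that within-arm pre-to-post change on these scales is descriptive, because it mixes discharge with the programme.

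The cost is two or three sentences, with no new data or visits and no change to the sample size. Adjustment uses at most one degree of freedom.

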Description of Sleep Health Using the Internet (SHUTi) program for CBT-I. The SHUTi program is an automated, interactive, internet-based intervention based on well-established face-to-face CBT-I components including sleep restriction, stimulus control, sleep hygiene, cognitive restructuring, and relapse prevention. It consists of six core areas of focus that include interactive educational content and case studies about insomnia and its precipitating factors. These cores are designed to parallel traditional (in-person) CBT-I sessions and are “metered;” that is, new cores are available seven days after completion of the previous core. The program includes a variety of interactive features, including goal-setting, feedback based on user-identified symptoms, animations, quizzes, vignettes, and video-based expert explanations. SHUTi was developed based on the Model for Internet Interventions (a-Ritterband, et al., 2009). SHUTi users must fill out at least five daily sleep diaries for each core in seven days in order to access subsequent cores. Sleep diary input is crucial in the customization of the program based on individual situations.

SHUTi is considered a NSR IDE device as it is **not** being used in the indications as set forth:

- as an implant and presents a potential for serious risk to the health, safety, or welfare of a subject;
- purported or represented to be for use supporting or sustaining human life and presents a potential for serious risk to the health, safety, or welfare of a subject;
- for a use of substantial importance in diagnosing, curing, mitigating, or treating disease, or otherwise preventing impairment of human health and presents a potential for serious risk to the health, safety, or welfare of a subject; or
- Otherwise presents a potential for serious risk to the health, safety, or welfare of a subject”.

Protocol Number: 18-CC-0079

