Pittsburgh Sleep Quality Index (PSQI). The Pittsburgh Sleep Quality Index (PSQI) is a 19-item, self-rated questionnaire used to measure sleep quality and disturbances over a 30-day time interval. Nineteen individual items generate seven "component" scores: subjective sleep quality, sleep latency, sleep duration, habitual sleep efficiency, sleep disturbances, use of sleeping medication, and daytime dysfunction. A global summation score of five or higher is indicative of poor sleep quality (Buysse, Reynolds, Monk, Berman, & Kupfer, 1989). The PSQI has been validated in populations with insomnia and other sleep disorders, with psychiatric patients, and in normal populations (Backhaus, Junghanns, Brooks, Riemann, & Hohagen, 2002; Doi, Minowa, Uchiyama, Okawa, Kim, Shibui, & Kamei, 2000). There exists some early evidence of validity in alcohol-dependent populations (Brooks, Krumlauf, Whiting, Clark, & Wallen, 2012; Wallen et al., 2014). The PSQI has internal consistency and a reliability coefficient ranging from 0.80 to 0.83 for its seven components (Buysee, et al., 1989; Carpenter & Andrykowski, 1998). It takes approximately five minutes to complete. Phase I and II participants will complete the PSQI at the pre- mid-point, and post-test.

The Multidimensional Fatigue Symptom Inventory-Short Form (MFSI-SF). The MFSI-SF (Stein 2004), which is a 30-item measure, was used in the 2012 study by Ritterband and colleagues that demonstrated the efficacy of internet-delivered CBT-I for cancer survivors. This measure has also been used in relation to insomnia and internet-based delivery of CBT-I by Thorndike and colleagues in 2013. A

Protocol Number: 18-CC-0079

review by Donovan and colleagues (2015) reported that the measure has been used in a variety of study designs, including longitudinal, cross-sectional, and randomized control trials, with acceptable psychometric properties.

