Composite Scale of Morningness (CSM). The Composite Scale of Morningness is a 13-item scale (Smith, Reilly, & Midkiff 1989). Questions address topics like morning affect, preferred sleep/wake times, and peak cognitive performance, with scores ranging from 13 (reflecting "eveningness") to 55 (reflecting "morningness"). The CSM typically shows relatively high internal consistency (Cronbach's alpha > 0.8) (Di Milia, Adan, Natale, & Randler 2013).

We will pull additional data from the screening/treatment protocol to characterize our sample and conduct exploratory analysis based on the aforementioned aims, including but not limited to:

- Childhood Trauma Questionnaire (CTQ)
- Structured Clinical Interview for Diagnostic and Statistical Manual of Mental Disorders (DSM-IV or DSM-5) (SCID)
- Clinical Institute Withdrawal Assessment – Alcohol revised (CIWA-Ar)
- Comprehensive Psychopathological Rating Scale (CPRS)

[figure not shown]

Figure 1: Study flow chart

Participants will be screened for eligibility on or after day 14 of inpatient treatment. Days 14-21 will be when the participant is consented, screened for OSA (after consent), randomized (if they meet inclusion requirements), and begin daily diary assessments as a baseline measure. If they are discharged before they are deemed eligible for continue study participation and randomized to a group, they will be removed from the study.

Table of Measures						
	Inpatient			Outpatient		
	Pre-Test (Before SHUT-i® Intervention or Education only program initiation)	Start SHUT-i® Intervention or Education only program	Prior to or within 2 weeks of Discharge	3-4 weeks after SHUT-i® Intervention or Education only program initiation	Post-Test (After SHUT-i® Intervention or Education only program completion)	6-7 months post-discharge (clinic visit or by phone)
ISI				X		X
PACS					X	X
PSQI	X			X	X	
DBAS-16	X				X	
FOSQ-10	X				X	
SE-S	X				X	
IDS	X				X	
ESS	X				X	
Trait Anxiety Inventory	X				X	
CSM	X					
MFSI-SF	X				X	
At least 4 days, 3 nights (Phase I)/1 week (Phase II) of actigraphy assessment	X			X	X	
Sleep Diaries	X			X	X	
Start SHUTi (Phase I and II) or education only (Phase II only) program		X				
Abbreviated Internet Evaluation and Utility Questionnaire (Phase I only)			X			

Protocol Number: 18-CC-0079

Internet Impact and Effectiveness Questionnaire, Internet Evaluation and Utility Questionnaire, and the Internet Intervention Adherence Questionnaire (Phase I and II)					X	

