2.5.3 Justification for certain inclusion/exclusion criteria

*Morin, Belleville, Bélanger, and Ivers (2011) recommend an ISI cutoff score of at least 10 in detecting clinical insomnia while preserving very good specificity and sensitivity in a population-based or clinical trial sample.

One of SHUT-I's potential side effects from its sleep restriction phase is increased daytime sleepiness. Increased daytime sleepiness is associated with increased frequency of falls in the elderly (individuals >65 years old) (Helbig et al., 2013), thus we are excluding individuals over the age of 65.

Protocol Number: 18-CC-0079

Among individuals who are alcohol-dependent with untreated moderate-severe OSA, sleep restriction may further increase sympathetic and stress response, leading to an increased risk of cardiovascular adverse events (Irwin & Ziegler, 2005). Severe OSA is associated with increased daytime sleepiness, motor vehicle crashes, depression, cardiovascular and cerebral morbidity and mortality, cognitive and metabolic dysfunction (Peppard & Hagen, 2017). Thus, we are excluding individuals with untreated moderate-severe OSA.

A study by Pacek, Herrmann, Smith, and Vandrey (2017) reported that participants reported sleep difficulties with abstinence from cannabis and resulted in the relapse in cannabis use at a later time. It is unclear whether sleep difficulty symptoms improve with relapse, but the authors also point out that cannabis use contributes to observed sleep difficulties. Whether or not disordered sleep contributes to long-term cannabis use is unclear (Pacek, Herrmann, Smith, & Vandrey, 2017). Finally, cannabis is independently associated with impairment of sleep continuity (Pacek et al., 2017). Thus, we are excluding participants who meet the criteria SCID-5/DSM-5 criteria for severe cannabis use disorder.

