5.3 Justification for exclusion of vulnerable populations

Vulnerable populations (including individuals who are pregnant, cognitively impaired, children, and prisoners) will not be enrolled in this study as they are ineligible for admission under the screening and assessment protocol (14-AA-0181).

6 Evaluation of Risks/Discomforts and Benefits ratio:

- a. **Benefits:** This study will provide pilot data on the feasibility, acceptability, and efficacy of an internet-based CBT-I program undergoing inpatient treatment AUD. The program may represent an efficacious non-pharmacologic intervention for insomnia in this population, potentially decreasing medication intervention. It is possible that there may be no direct benefit to the participant. However, based on prior literature, we anticipate alleviation or decrease in insomnia in some study participants.
- b. **Risks:** It is possible that answering some of the questionnaires may cause discomfort to participants. Participants may feel uncomfortable wearing the WatchPAT device or the actiwatch device to sleep. Participants may potentially experience a rash and/or pruritus in wearing the WatchPAT or actiwatch. During WatchPAT testing, participants might also experience slight pressure around their finger that is being used for the test. After WatchPAT testing, participants might notice proximal nail fold redness and a few may experience proximal nail fold blister on the finger that is being tested. These side effects will usually resolve within 24-48 hours after the test. Participants will be instructed to report any untoward side effects from WatchPAT testing to the 1SE inpatient unit's clinical staff and to the research team. 1SE clinical staff will monitor the progression of these side effects and treat as necessary. Participants will also be made aware that they can always stop the WatchPAT testing at any time for any reason. Participants in Phase I and those assigned to the SHUTi condition in Phase II may experience daytime sleepiness (and potentially impaired daytime functioning) during the sleep restriction part of the program, particularly if they are taking medications with side effects of drowsiness during the study period.
- c. **Alternative treatments and procedures:** The alternative to participating in this study is not to participate and obtain treatment as usual.

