- d. **Procedures for protecting/minimizing risk:** Every effort will be made to address and minimize participant discomfort including scheduling a repeat session or postponing study procedures if a participant becomes uncomfortable. Confidentiality and information technology standards are in place at the intramural programs of the NIH campus to protect electronic repositories of patient data. We selected a minimally-

Protocol Number: 18-CC-0079

invasive diagnostic tool to assess for OSA, requiring only one night of sleeping with the device. It is reasonably expected that these safeguards will protect participants' medical and personal health information, ensuring their privacy. Participants exhibiting excessive sleepiness will be counseled to avoid activities (e.g. drowsy driving and/or using the stove) that will jeopardize their safety and the safety of others.

- e. **Provisions for ensuring that necessary medical or professional intervention is available in the case of adverse events to the subjects:** The MAI will be made aware of any adverse events to participants directly related to this protocol.

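### The Epworth Sleepiness Scale is given only before and after the program, so the planned comparison of daytime sleepiness between arms can miss a rise during SHUTi's sleep restriction

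*Combined protocol and SAP*

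**What the plan says.** Section 2.5.3 states that one of SHUTi's "potential side effects from its sleep restriction phase is increased daytime sleepiness", and excludes people over 65 for that reason. Section 6 (b, Risks) says that SHUTi participants "may experience daytime sleepiness (and potentially impaired daytime functioning) during the sleep restriction part of the program". Section 6 (d) adds: "Participants exhibiting excessive sleepiness will be counseled to avoid activities", with drowsy driving as one example. It names no instrument or threshold for finding these people.

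Section 2.4 describes the ESS as a measure of the "general level of excessive daytime sleepiness over a one week time period", taking two to three minutes, with a score above ten indicating excessive sleepiness. Its text gives no schedule. The Table of Measures marks it at pre-test and in the column "Post-Test (After SHUT-i® Intervention or Education only program completion", and not at 3-4 weeks.

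Section 1.2 lists daytime sleepiness among the secondary outcomes to be compared between SHUTi and education-only. Section 3 tests secondary objectives with a mixed model for repeated measures.

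**The concern.** The protocol ties the risk to a particular part of treatment, but its one sleepiness scale is used only outside treatment. Sleepiness that lasts to post-test would show in the planned ESS comparison. Sleepiness that rises under sleep restriction and settles by completion might not, and the trial could then understate the daytime cost of SHUTi.

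There is also a practical side. Most of the program is completed as an outpatient. The counseling in Section 6 (d) depends on someone noticing sleepiness, and no sleepiness score is collected in those weeks to help.

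**Working it through.** **1. Is the ESS schedule read correctly?** It rests on the table, so its rows were checked against the text of Section 2.4.
- FOSQ-10: same two marks as the ESS. The text agrees: "The FOSQ-10 will be administered at pre- and post-test time points".
- PSQI: marked at pre-test, 3-4 weeks and post-test. The text agrees: "Phase I and II participants will complete the PSQI at the pre- mid-point, and post-test".
- ISI: the row as extracted lacks the pre- and post-test marks that the text gives, so the table is not flawless.
- DBAS-16, SE-S, IDS, Trait Anxiety Inventory and MFSI-SF have the same two marks as the ESS.

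The pre-and-post reading is the natural one.

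**2. Does the 3-4 week assessment fall inside treatment?** Section 1 says that "new cores are available seven days after completion of the previous core". Counting the start as day 0, the six cores open at the earliest on days 0, 7, 14, 21, 28 and 35. At days 21-28, core 4 or 5 is the latest that can be open, and core 6 cannot be. The assessment is therefore inside the program for every SHUTi participant still using it.

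**3. Can the post-test ESS look back that far?** Completion comes on day 35 at the earliest. One week of recall reaches back to day 35 - 7 = 28, the far edge of the 3-4 week window, and no further.

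**4. What else is collected during treatment?**
- Diaries (Section 2.4): naps and open comments. No sleepiness rating is listed.
- ISI: at mid-point in both arms, and at the start of each core in SHUTi only.
- PSQI at mid-point: a daytime-dysfunction component with 30-day recall. At days 21-28 this reaches back to 9 to 2 days before the program began, so it covers all treatment so far.

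All bear on daytime state, but none is a sleepiness scale.

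**5. How many would contribute?** Section 3 states a detectable effect of 0.84 with 60 participants, 40% attrition, correlation 0.6, two-sided alpha 0.05 and power 0.80. This reproduces:
- Completers: 60 × 0.6 = 36, or 18 per arm.
- SD of change: √(2(1 - 0.6)) = √0.8 = 0.894 SD units.
- Detectable effect: (1.960 + 0.842) × 0.894 × √(2/18) = 0.835.

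The 24 participants lost (0.40 × 60) would have no ESS after pre-test. The documents do not say when they leave, so a mid-point ESS would recover a value for 0 to 24 of them, giving 18 to 30 per arm.

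**6. How precise would the mid-point estimate be?** The half-width of the 95% CI for the difference, adjusted for pre-test, is t(0.975, 2n - 3) × SD × √(1 - r²) × √(2/n). The documents give no SD or correlation for the ESS. An SD of 4-5 is assumed, and r = 0.6 is borrowed from the plan's ISI figure.

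| n per arm | r = 0.6, SD 4 | r = 0.6, SD 5 | Range: r = 0.7, SD 4 to r = 0.4, SD 5 |
|---|---|---|---|
| 18 | 2.17 | 2.71 | 1.94 to 3.11 |
| 30 | 1.65 | 2.07 | 1.48 to 2.37 |

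For example, n = 18, SD 4: 2.035 × 4 × 0.8 × 0.333 = 2.17.

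For the share above 10, assumed to be 20-40%, the half-width is 1.96 × √(2p(1 - p)/n). This gives 26 to 32 percentage points with 18 per arm and 20 to 25 with 30.

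**The case against.** The plan already covers more than the ESS row suggests. Daytime sleepiness is compared by arm. Section 2.4 makes all other diary variables secondary outcomes, which brings naps under the same comparison. SHUTi users must complete at least five diaries per core to progress, so diaries run through treatment, and the ISI is repeated at every core. Section 7 provides continuous monitoring of side effects by the PI, Section 9 allows withdrawal where CBT-I is judged hazardous, and people over 65 or with moderate to severe sleep apnea are excluded. The benefit is also uncertain: the documents do not say which weeks hold sleep restriction, so a one-week ESS at weeks 3-4 could miss an earlier peak, and the intervals are wide.

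All of this stands, and it narrows the gap to one thing: no direct sleepiness measure during treatment. It does not close that gap. Naps and general daytime dysfunction are proxies, the core-by-core ISI exists in one arm only, and the monitoring provisions name no sleepiness instrument.

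A reader might go further and infer that no comparison of harms between arms is planned. Sections 1.2 and 3 do not support that, because the named harm is itself a compared secondary outcome. What is unstated is a tabulation of adverse events by arm. That is an optional reporting detail of little help here: Section 7 limits adverse events to related ones and defines them by criteria such as death, hospitalization or significant hazard. Section 8 does mention non-serious events, but ordinary sleepiness may seldom be recorded under the narrower definition.

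**Conclusion.** The point holds in a limited form. The planned ESS comparison is pre to post only, so it can miss sleepiness that rises during sleep restriction and eases by completion, and no direct sleepiness score is taken in the outpatient treatment weeks. This is an opportunity for a cheap improvement, not an error of analysis. No primary estimate, error rate or sample size changes.

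A mid-point ESS would support description only. With half-widths of about 1.7 to 2.7 points, or 20 to 32 percentage points for the share above 10, it can exclude only larger differences. Those figures rest on the assumed SD, correlation and share above 10, and on 18 to 30 participants per arm. The conclusion about the schedule rests on the Table of Measures and the seven-day spacing of cores. How far the 3-4 week assessment overlaps sleep restriction is unknown.

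**What to change.** Add the ESS to the 3-4 week assessment in both arms, and use the pre-test, mid-point and post-test values in the ESS mixed model. Suggested text for Section 3:

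> The SHUTi minus education difference in ESS at the 3-4 week assessment, adjusted for pre-test ESS, will be reported with a 95% confidence interval, together with the number in each arm scoring above 10. These are descriptive estimates, not tests.

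Add to Section 6 (d) that the mid-point ESS is scored when it is completed and that anyone above 10 receives the counseling described there. Without this step the form describes sleepiness but does not help the participant. Section 10 already has a research team member administer these assessments in person or by phone, so scoring at the time is feasible.

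If the form cannot be added, state before analysis that the mid-point PSQI daytime-dysfunction component and diary naps will be shown by arm. A table of adverse events by arm may be added, but is optional.

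Cost: 2-3 minutes per participant, at most 60 × 3 = 180 minutes (3 hours) in total, at an assessment where the PSQI and ISI are already completed, plus a short amendment and one table. Downsides: participants already past the mid-point would have no value, the intervals are wide, and an earlier peak could still be missed. A treatment-period value that is not collected cannot be recovered later.
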